2.4.3.3 Intravenous Fluid Nutritional Intake

Only fluid intake administered, energy intake administered, and carbohydrate intake administered will be calculated for intravenous fluid intake as protein and lipid intake are 0 g/mL. These will be calculated as follows:

Fluid intake administered (mL/kg/24 hours):

$$\frac{24 * \frac{Total \ volume \ administered(mL)}{Weight \ on \ that \ day(kg)}}{Total \ Infusion \ Duration \ (hours)}$$

Energy intake administered (kcal/kg/24 hours):

$$\frac{24 * 3.4 \left(\frac{kcal}{g}\right) * \frac{Percentage \ Dextrose * \frac{Total \ volume \ administered \ (mL)}{100}}{Weight \ on \ that \ day \ (kg)}}{Total \ Infusion \ Duration \ (hours)}$$

Carbohydrate intake administered (g/kg/24 hours):

24 * Percentage Dextrose * Weight	Total volume administered (mL)	
	100	
	Weight	t on that day (kg)
То	tal Infusio	n Duration (hours)

2.4.3.4 Overall Nutritional Intake

Overall nutritional intake (ordered and administered) will be calculated per patient per day for fluid intake and energy intake by summing the following:

PN Intake + EN intake + IV Fluid intake

The percentage of PN and EN for fluid and energy intake will be calculated as follows:

Percentage of PN administered:

 $\frac{Total \ PN \ intake \ administered}{Total \ overall \ intake \ administered} x100\%$

Percentage of EN administered:

 $\frac{Total \ EN \ intake \ administered}{Total \ overall \ intake \ administered} x100\%$

2.4.3.5 Growth

•

Weight at baseline and during treatment will be assessed daily and will be summarized on an approximately 15-day basis using descriptive summary statistics in each of the treatment groups.

Length or height (and head circumference for infants <1 year of age) will be assessed and summarized at baseline and approximately every 15 days up to end of study treatment using descriptive summary statistics (number of patients, mean, standard deviation, median, minimum, and maximum in each of the 2 treatment groups (Clinolipid vs Intralipid).

Growth will be assessed and evaluated from baseline to end of study treatment on an approximately every 15-day basis using descriptive summary statistics in each of the treatment group as follows:

• Gain in weight over last 15 days (g/kg/day in infants <1 year of age; i.e. the change between day 15 and baseline, day 30 and day 15, day 45 and day 30, etc):

Weight (g)on Day (X + 15) – Weight(g) on Day X
Weight (kg)on Day X
15
Gain in weight from baseline (g/kg/day in infants <1 year of age):
Weight (g)on Day X – Weight(g)at baseline
Weight (kg) at baseline
X

• Gain in weight over last 15 days (g/day in children and adolescents):

Weight (g) on Day $(X + 15) - We$	eight(g) on Day X
15	

• Gain in weight from baseline (g/day in children and adolescents):

$$\frac{Weight (g)on Day X - Weight(g) at baseline}{X}$$

 Gain in length/height over last 15 days (mm/week in all):
 Length (mm)on Day (X + 15) - Length (mm)on Day X 2.14

 $\frac{\text{Length (mm)on Day X - Length (mm) at baseline}}{X/7}$

• Gain in head circumference over last 15 days (mm/week in infants <1 year); Head circumference (mm)on Day (X + 15) – Head circumference (mm)on Day X

• Gain in head circumference from baseline (mm/week in infants <1 year); Head circumference (mm)on Day (X) – Head circumference (mm) at baseline

- Changes in the SDS from reference growth curves over last 15 days (Fenton growth curve for premature infants¹⁹, WHO growth standards²⁰ for infants and children ages 0 to 2 years, or CDC growth charts²¹ for children age \geq 2 years): SDS at Day (X + 15) – SDS at Day X
- Changes in the SDS from reference growth curves from baseline (Fenton growth curve for premature infants, WHO growth standards for infants and children ages 0 to 2 years, or CDC growth charts for children age ≥2 years):

SDS at Day X - SDS at baseline

Boxplots will also be given for each of the growth parameters by treatment group.

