7.2.3 Standard-of-Care Procedures

The following procedures will be performed at intervals determined by the SOC at each investigational site (refer to Appendix 1, Schedule of Events Table):

- Laboratory evaluations including:
 - hematology complete blood count
 - chemistry basic metabolic panel and electrolytes
- Diagnosis of neonatal morbidities including bronchopulmonary dysplasia (BPD), retinopathy of prematurity (ROP), intraventricular hemorrhage (IVH), periventricular leukomalacia (PVL), necrotizing enterocolitis (NEC), and late-onset sepsis in enrolled premature infants born at 24 to <37 weeks of gestation up to 1 month CA with a birth weight ≥750g.

7.2.4 Days 15, 30, 45, 60, 75 and 90 or End of Study Treatment Procedures

The Study Treatment Period starts when the patient receives study treatment. End of study treatment is defined as the last day of PN with Intralipid or Clinolipid; maximum 90 days of study treatment is allowed.

The following procedures will be performed approximately every 15 days ± 2 days for patients continuing on PN (days 15, 30, 45, 60, 75 and 90) and within ± 2 days of the last day of study treatment (maximum 90 days on either Clinolipid or Intralipid) whenever that occurs:

- Physical examination including weight, length or height (and head circumference for infants <1 year of age)
- Vital signs
- Concomitant medications
- Concomitant procedures
- AEs
- Laboratory evaluations including:
 - Hematology parameters
 - Serum chemistry parameters
 - Hepatic integrity parameters
 - Total and direct bilirubin
 - Triglyceride levels
 - FA profile
 - Holman Index
 - Phytosterol, cholesterol, and squalene levels

In addition, the following data will be collected at end of study treatment:

 Diagnosis of neonatal morbidities including bronchopulmonary dysplasia (BPD), retinopathy of prematurity (ROP), intraventricular hemorrhage (IVH), periventricular leukomalacia (PVL), necrotizing enterocolitis (NEC), and lateonset sepsis in enrolled premature infants born <37 weeks of gestation up to 1 month CA.

After end of study treatment (maximum of 90 days), the patient will receive nutritional intervention as prescribed by their healthcare provider as SOC if PN is still required.

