1.4.2 Determination of Sample Size

The sample size of 100 patients (50 in each of the 2 treatment groups: Clinolipid vs Intralipid), including neonates, is based on the feasibility of timely enrollment of patients for generating reference data and summary descriptive statistics, rather than on a formal power calculation. No formal hypothesis testing is planned.

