2.1.2 Visit Windows

The study visits can be obtained from the eCRF and need not be derived programmatically. The visits will be displayed as: Screening, Day 1 (Baseline), Day 2, ... Day 14, Day 15, Day 30, Day 45, Day 60, Day 75, Day 90/End of treatment (EOT).

Results from unscheduled visits will not be included in table summaries. These values will only be presented in the listings.

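### SAP 2.4.3.5 divides growth changes by nominal time, not elapsed time, and gives no rule for a shortened last interval

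*SAP*

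**What the plan says.** SAP 2.4.3.5 brings the end of treatment into scope: "Growth will be assessed and evaluated from baseline to end of study treatment on an approximately every 15-day basis". It then defines two families of rates.

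- **Interval rates.** For weight the quantity is "Gain in weight over last 15 days (g/kg/day in infants <1 year of age", explained as "i.e. the change between day 15 and baseline, day 30 and day 15" and so on, and the change is divided by 15. The g/day version for children and adolescents also divides by 15. For length the extracted formula reads "Length (mm)on Day (X + 15) - Length (mm)on Day X 2.14", where 2.14 is the divisor in weeks.
- **From-baseline rates.** The change is divided by X for weight and by X/7 for length. X appears only as Day X and is not defined.

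No growth formula contains a measurement date.

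The timing rules sit elsewhere. Protocol 7.2.4 schedules these assessments "approximately every 15 days ± 2 days for patients continuing on PN" and again within 2 days of the last treatment day, whenever that falls. The protocol synopsis gives a treatment duration of 7 to 90 days. SAP 2.1.2 takes visits from the eCRF without programmed windows and gives the last one a pooled label: "Day 75, Day 90/End of treatment (EOT". SAP 1.4.1 makes the first treatment day study Day 1. Protocol 6.5 has weight recorded daily, but length and head circumference only about every 15 days.

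**The concern.** The outputs are labelled g/kg/day, g/day and mm/week, so a reader will take them as change per unit of elapsed time. They are that only when the true gap equals the nominal one. The visit window, the Day 1 baseline and above all an early end of treatment can break that equality.

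Growth is one of the two components of the nutritional-adequacy secondary endpoint, the other being intake. A fixed divisor applied to a shortened last interval always pulls the rate toward zero, and more so the earlier the patient stops. If duration of parenteral nutrition differed between arms, that would appear as a difference in growth. The SAP also leaves the handling of early stoppers to the programmer: one could insert the end-of-treatment value, another could drop the interval because no Day X+15 value exists.

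**Working it through.** **The plan's own figure.** 15/7 = 2.143, which rounds to 2.14. The length divisor is therefore the nominal 15 days expressed in weeks.

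**Formula.** Reported rate = change / divisor. True average rate = change / elapsed days. So reported/true = elapsed days / divisor in days. This holds for any change and needs no assumption that growth is linear.

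**Inputs.** Window of ±2 days per visit (Protocol 7.2.4). Day 1 is the first treatment day (SAP 1.4.1). Treatment lasts 7 to 90 days (Protocol synopsis). Divisors are from SAP 2.4.3.5. The end-of-treatment days below are examples.

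| Case | Elapsed days | Divisor (days) | Reported/true |
|---|---|---|---|
| Length, first visit 2 days late, next 2 days early | 15 − 4 = 11 | 15 | 0.73 (−27%) |
| Length, first visit 2 days early, next 2 days late | 15 + 4 = 19 | 15 | 1.27 (+27%) |
| Weight, Day 15 to Day 30, weights from those exact days | 15 | 15 | 1.00 |
| First interval, baseline on Day 1, visit on Day 15 | 14 | 15 | 0.93 (−6.7%) |
| First interval, baseline the day before, visit on Day 15 | 15 | 15 | 1.00 |
| Last interval, end on Day 20 after a Day 15 visit | 5 | 15 | 0.33 |
| Last interval, end on Day 7, baseline on Day 1 | 6 | 15 | 0.40 |
| From baseline, end on Day 20, X = 90 | 19 | 90 | 0.21 |
| From baseline, end on Day 20, X = 20 | 19 | 20 | 0.95 |
| From baseline, end on Day 7, X = 7 | 6 | 7 | 0.86 |
| From baseline, end on Day 90, X = 90 | 89 | 90 | 0.99 |

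The two last-interval rows assume that the end-of-treatment value is used as the Day X+15 value. The from-baseline rows assume baseline on Day 1.

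**Comparison within the SAP.** Actual dates are used for patient days at risk of EFAD (2.4.1.1), time to PNALD (2.4.2.2.1), days to the maximal liver value (2.4.2.3) and the adverse event rate (2.5.1.1). Growth is the exception.

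**The case against.** Several stronger readings are tempting, and the documents do not support them.

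- **All growth rates, weight included, may be off by 27%.** The window bears mainly on length. With daily weights taken on the exact study days, mid-study weight intervals are exact. Even for length, 27% needs two adjacent visits at opposite window limits, and errors in both directions partly cancel in group means.
- **The SAP divides by 90 for everyone at end of treatment.** It never says so. The pooled label in SAP 2.1.2 makes that reading possible, but actual study day is just as natural a meaning of Day X. On that meaning the from-baseline error is about one day, 1% to 14%.
- **An early end of treatment is always divided by 15.** The interval formula covers Day X and Day X+15 only. For a patient ending on Day 20 the interval might be treated as not evaluable. For weight, the heading could be taken literally as Day 20 minus Day 5, which is exact. The 33% figure rests on one plausible way of filling the gap.
- **The first interval is always 14 days.** Protocol 7.2.1 allows non-laboratory baseline procedures up to 24 hours before treatment. If they fall on the previous calendar day, there is no error at a Day 15 visit.
- **The arms are compared unfairly.** The same formulas apply to both arms, and nothing in the documents shows that duration will differ.

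It is also fair to say that the study is descriptive: the sample size rests on feasibility "rather than on a formal power calculation. No formal hypothesis testing is planned". Growth is summarised only on an approximately 15-day basis.

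These points limit the size and certainty of the error. They do not supply a divisor for a shortened interval, a definition of X, or a reason to use nominal time when elapsed time can be computed.

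**Conclusion.** The point stands in this limited form. SAP 2.4.3.5 uses nominal time as the divisor, leaves X undefined and has no end-of-treatment rule.

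The error in an individual length rate is up to 27% either way. It is 6.7% in the first interval when baseline is on Day 1 and the visit on Day 15. It can be much larger for a patient who stops early, but only on stated conditions: the 33% figure needs the end-of-treatment value to close the last interval, and the 21% figure needs X to be read as 90.

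Bias between arms would arise only if treatment duration differs by arm. The primary EFAD endpoint is untouched. No divisor error is claimed for head circumference, because those divisors are not legible in the extracted text, or for SDS changes, which are differences and not rates.

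**What to change.** Amend SAP 2.4.3.5 as follows.

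1. For every growth rate, including end of treatment, divide by (date of current measurement − date of previous or baseline measurement) in days, or by that number / 7 for mm/week.
2. State that the last interval runs from the last scheduled measurement to end of treatment.
3. Do not carry over the + 1 used in the SAP's other date formulas. That convention counts days inclusively and would turn the 14 days from Day 1 to Day 15 back into 15.

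Once elapsed days are used, the ratio is 1.00 in every row of the table and X is no longer needed as a divisor. The cost is a formula edit and the matching programming before unblinding. It relies on measurement dates held in the study data and needs no new procedure or visit.

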2.2 Secondary Objective(s)

The secondary objectives in patients receiving either Clinolipid or Intralipid are to evaluate:

- The risk of developing liver disease including PNALD:
 - PNALD will be defined by direct bilirubin ≥2 mg/dL when no other etiology for liver dysfunction is present;
 - Hepatic integrity will be assessed by measuring plasma liver function tests: alkaline phosphatase (ALP), aspartate aminotransferase (AST), alanine aminotransferase (ALT), gamma-glutamyl transferase (GGT), and total and direct bilirubin;
 - Plasma main phytosterols (stigmasterol, campesterol, sitosterol), cholesterol and squalene levels will be assessed. Phytosterols levels will be correlated with the risk of developing PNALD.
- The adequacy of nutritional interventions:
 - Prescribed and actual nutritional intakes (energy, protein, carbohydrates, and lipid) from both PN and enteral/oral nutrition will be collected and recorded on a daily basis and summarized on a daily basis during the first 2 weeks of treatment and on an approximately 15-day basis afterwards up to the end of study treatment in each of the treatment groups.
 - Growth will be assessed and evaluated from baseline to end of study treatment on an approximately every 15-day basis using descriptive summary statistics for weight, and height/length (and head circumference in infant <1 year) in each of the treatment groups as follows:
 - Gain in weight (g/kg/day in infants <1 year of age, g/day in children and adolescents) and gain in length/height (mm/week in all) and head circumference (mm/week in infants <1 year);
 - Changes in the standard deviation score (SDS or z-score) from reference growth curves (Fenton growth curve for premature infants, World Health Organization (WHO) growth standards for infants and children ages 0 to 2 years, or Center for Disease Control (CDC) growth charts for children age ≥2 years).

- The safety profiles of Clinolipid and Intralipid, as assessed by adverse events (AEs), serious adverse events (SAEs) and AEs of special interest (AESIs)

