1.4 Study Design

1.4.1 Overall Study Design and Plan

This is a multi-center, randomized, double-blind, controlled, safety and efficacy study to evaluate the occurrence of EFAD (diagnosed by Holman Index >0.4) in pediatric patients receiving either Clinolipid or standard-of-care soybean oil-based ILE (Intralipid) in the hospital setting from 7 up to 90 days as part of PN. The risk of developing liver disease, including PNALD (defined by direct bilirubin $\geq 2 \text{ mg/dL}$) when no other etiology for liver dysfunction is present, also will be assessed.

Approximately 100 pediatric patients, including neonates, will participate in the study. Patients will be randomized in a 1:1 ratio to the treatment groups (Clinolipid or Intralipid) according to a central dynamic randomization scheme stratified by site and age group (premature infants born <37 weeks of gestation, full-term neonates born \geq 37 weeks of gestation to <1 month of age, infants 1 to <12 months of age, children 1 to <10 years of age, adolescent 10 to <18 years of age). In the case of multiple birth pregnancies, the infants will be assigned to the same treatment group.

Holman Index and FA profile will be evaluated. Select polymorphisms in the FA desaturase genes FADS1 and FADS2, will be determined in a subset of patients. The major plasma phytosterols found in the ILEs (stigmasterol, campesterol, sitosterol), cholesterol, and squalene will also be assessed.

The study consists of a Screening Period to confirm the patient's eligibility for the study after the informed consent form (ICF) and assent (if applicable) is signed and a Treatment Period, where study Day 1 is defined as the first day the patient receives study treatment.

End of study treatment is defined as the last day of PN with Intralipid or Clinolipid; maximum 90 days of study treatment is allowed.

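### SAP 2.4.3.5: the from-baseline weight gain in g/kg/day divides by baseline weight at every visit, so a constant growth rate reads higher the longer the infant is treated, and the merged Day 90/EOT row mixes values that are not comparable

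*SAP*

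**What the plan says.** The protocol fixes only the unit. Section 2.2 asks for "Gain in weight (g/kg/day in infants <1 year of age, g/day in children and adolescents", and section 9.6.2.2 repeats it. Neither says which weight should divide the gain.

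SAP 2.4.3.5 supplies the formula. For the measure it lists as "Gain in weight from baseline (g/kg/day in infants <1 year of age", the numerator is "Weight (g)on Day X – Weight(g)at baseline", the divisor is "Weight (kg) at baseline", and the result is divided by X. The divisor weight stays the same for every X.

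The same section defines two companion measures:
- a gain over the last 15 days ("i.e. the change between day 15 and baseline, day 30 and day 15, day 45 and day 30, etc"), whose divisor is reset to the weight at the start of each interval;
- changes in SDS, both over the last 15 days and from baseline.

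SAP 2.1.2 lists the visits after Day 14 as "Day 15, Day 30, Day 45, Day 60, Day 75, Day 90/End of treatment (EOT", so the last scheduled visit and the end of treatment share one row. SAP 1.4.1 sets the upper limit on X ("maximum 90 days of study treatment is allowed") and the day numbering ("study Day 1 is defined as the first day the patient receives study treatment"). SAP 1.4.2 plans no hypothesis tests.

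**The concern.** A rate per kilogram per day is read as growth relative to the weight the infant has while growing. Dividing by a weight that may be up to 90 days old turns a constant fractional rate into a rising one. Two displays are affected.

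- **Trend across visits.** The from-baseline row would suggest accelerating growth in infants whose fractional rate has not changed. It can also hide slowing. An infant who gains a fixed 15 g per kg of baseline weight each day reads 15 at every visit. By Day 90 that infant weighs 1 + 0.015 × 90 = 2.35 times baseline and is gaining 15/2.35 = 6.4 g per kg of current weight.
- **The Day 90/EOT row.** Treatment can last from 7 to 90 days, so X differs between infants in this row, and the SAP does not say which X applies. Infants with the same true rate get different values because they were treated for different times.

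Growth is part of the secondary endpoint on nutritional adequacy, and the protocol evaluates it from baseline to the end of treatment. The EOT row is therefore one that readers will look at.

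**Working it through.** The plan gives no growth figure to reproduce.

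**Inputs.** From SAP 2.4.3.5: the formula. From SAP 2.1.2: X = 15, 30, 45, 60, 75 and 90/EOT. Assumed: constant daily growth by a fraction g of current weight, with g = 0.010, 0.015 or 0.020.

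**Step 1: the SAP formula.** With W_X = W_0(1 + g)^X, the reported value is 1000 × ((1 + g)^X − 1)/X. The alternative is the log form, 1000 × ln(W_X/W_0)/X.

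| X | W_X/W_0 at 15 | SAP, true 10 | SAP, true 15 | SAP, true 20 | Log form, true 15 |
|---|---|---|---|---|---|
| 15 | 1.25 | 10.7 | 16.7 | 23.1 | 14.9 |
| 30 | 1.56 | 11.6 | 18.8 | 27.0 | 14.9 |
| 45 | 1.95 | 12.6 | 21.2 | 32.0 | 14.9 |
| 60 | 2.44 | 13.6 | 24.1 | 38.0 | 14.9 |
| 75 | 3.05 | 14.8 | 27.4 | 45.5 | 14.9 |
| 90 | 3.82 | 16.1 | 31.3 | 54.9 | 14.9 |

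At a true 15 the overstatement goes from 16.7/15 = 1.11 to 31.3/15 = 2.09. At a true 5 the formula gives 5.2 at Day 15 and 6.3 at Day 90.

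**Step 2: day counting.** Day 1 is the first treatment day, so Day X may be only X − 1 days after baseline. With X − 1 days of growth divided by X, a true 15 reads 15.5 at Day 15 and 30.7 at Day 90. The drift does not come from the day count.

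**Step 3: the EOT row, with X taken as days treated.**
- True 15, stop at Day 20: 1000 × (1.015^20 − 1)/20 = 17.3.
- True 15, stop at Day 40: 1000 × (1.015^40 − 1)/40 = 20.4, a gap of 3.0 at the same true rate.
- True 14, stop at Day 40: 1000 × (1.014^40 − 1)/40 = 18.6. The slower grower ranks above the true 15 that stopped at Day 20.

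If X were instead held at 90 for everyone in the row, a true 15 stopping at Day 20 would read 1000 × (1.015^20 − 1)/90 = 3.9. The choice of X therefore has to be written down.

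**Step 4: a fixed visit.** True 15 against true 14 gives 16.7 and 15.5 at Day 15. With 90 days for both, it gives 31.3 and 27.7. The order is kept, but the true difference of 1 becomes 1.2 and 3.6.

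**Step 5: the 15-day interval formula.** At a true 15, 1000 × (1.015^15 − 1)/15 = 16.7 in every full interval. That is a constant overstatement of about 11%, with no drift.

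**Step 6: other possible replacements.** Dividing by the mean of the start and end weights gives 14.8 at Day 15 but 13.0 at Day 90 for a true 15, and 19.7 falling to 15.8 for a true 20. Averaging consecutive interval rates returns 16.7.

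**The case against.** A reader might infer that arms with different PN duration cannot be compared on growth at all. The documents do not support that. At Days 15 to 75 both arms share X, so the formula favours neither and the order of rates is kept. Differential dropout could still change who contributes at a visit, but that is a separate matter. SAP 2.4.3.5 also plans the interval gain and the SDS changes, and neither carries this drift.

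A reader might also take the interval formula to have the same fault on a smaller scale. It does not: its offset is the same in every full interval.

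A third tempting step is to say that the EOT row will be biased against Clinolipid, because Protocol 6.14 discontinues Clinolipid patients who need Intralipid as rescue. The mechanism is in the text. But Protocol 6.8.3 ties the switch to EFAD that persists despite maximal lipid intake, and no rescue rate is given, so neither the occurrence nor the size of such a bias can be stated.

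The growth rates are assumptions. A true 15 held for 90 days needs weight to reach 3.8 times baseline, and a true 20 needs 5.9 times; at lower rates the drift is small. If growth were linear in baseline weight, the SAP formula would be flat. The study is descriptive, and this is one of several growth summaries.

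All of this limits the point. It does not remove the trend across visits or the mixing of durations in the Day 90/EOT row.

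**Conclusion.** The point holds within limits. Under constant fractional growth the from-baseline g/kg/day value rises with X: from 16.7 to 31.3 between Day 15 and Day 90 at an assumed 15, and from 10.7 to 16.1 at an assumed 10. Its trend across visits should not be read as a change in growth rate. Its Day 90/EOT row should not be compared between infants or between arms, because differences in duration can reverse the order (18.6 for a true 14 against 17.3 for a true 15).

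The conclusion does not extend to the order of rates at the fixed visits, to the 15-day interval gain or to the SDS changes. It rests on the assumed rates and on growth proportional to current weight. For a descriptive secondary endpoint the severity is minor to moderate.

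**What to change.** In SAP 2.4.3.5, replace the from-baseline g/kg/day formula with 1000 × ln(W_X/W_0)/(actual elapsed days from the baseline weight to the weight used). State that in the Day 90/EOT row each infant's own elapsed days apply. Preferably use the same log form for the 15-day interval measure, so that the two rows are on one scale and the offset of about 11% goes. This would also cover a final interval shorter than 15 days, for which the SAP gives no rule.

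The mean-weight denominator and the average of interval rates should not be treated as equivalents: the first drifts downward and the second keeps the 16.7.

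The protocol fixes only the unit, so an SAP edit appears sufficient. Weights are already recorded daily, and the cost is one formula (two if the interval measure is changed) and its programming. The downside is that reported gains will be lower. Under linear growth the log form also falls over time: for 15 g per kg of baseline weight per day it gives 1000 × ln(1.225)/15 = 13.5 at Day 15 and 1000 × ln(2.35)/90 = 9.5 at Day 90. That reflects a real slowing relative to current weight, and a table footnote should say so.
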